Using this approach, it is expected to address the informatics challenge of determining how to design information technology that improves engagement and clinical outcomes for patients who require continuous monitoring and who engage an informal caregiver in self-management outside clinical settings. Our work extends the design of remote-monitoring systems from stationary, home-based systems to wearable devices that patients can engage with throughout an active day in the community. Our research team—which consists in a biomedical systems engineer, a human factors engineer specialized in consumer health informatics, a pediatric endocrinologist, and a pediatrician specialized in clinical research — works in alliance with the Center for Diabetes Technology at the University of Virginia. Study team members have developed this ambulatory platform that will be used as the foundation for this study.

Rationale: The hypothesis of this study is that individuals randomized to the CGM/Fitbit with no weekly feedback (Control Group) will improve management modestly initially (as a result of either of new access to CGM or the Hawthorne effect of being studied), but their measures of engagement (patient self-management behavior (i.e. personal insulin parameters) and diabetes-related dyad communication) will return to baseline levels by the 12-week evaluation. By contrast, it is hypothesize that individuals randomized to CloudConnect (Experimental Group) will have a greater increase in engagement and dyad communication by 8 weeks that is sustained by 12 weeks (3 months).

It is further hypothesize that adolescents randomized to CloudConnect will have a lowering of HbA1c that is related to the increase in dyad disease-specific engagement. Moreover, our hypotheses are that this unique self-management approach in T1D will increase engagement of adolescents and their informal caregiver through increased communication and self-management behavior, and that this increase in engagement will lead to improved medical outcomes.

These hypotheses are based on data from preliminary studies collected by the study group and the literature. This preliminary data support that parents of adolescents with T1D are eager to follow their child's blood

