This is a randomized control, open-label, single-site clinical trial. We will target completion by eighty adolescents (age 12-17 years) with Type 1 diabetes and their parent/guardian (age 18+) to participate in a 3 month outpatient study. Participants will be randomized to either a Control Group or Experimental Group. Both groups will use the study continuous glucose monitor, study activity tracker, and a study insulin pen if an multiple daily injection (MDI) user. Subjects who use an insulin pump to treat their type 1 diabetes will use their personal insulin pump. All subjects will be asked to download this equipment and provide it to the study team each week. The study team will communicate weekly with each group. Questionnaires will also be completed at the beginning and at the end of the study. The Experimental Group will receive the CloudConnect Reports. The Control Group will not receive this feedback.

3. Does the study involve a placebo?

No

Human Participants

Ages: 12-17 years old and at least one of parent(s)/guardian(s) (age 18+)/guardian (adolescent/parent dyad is required for participation in this trial)

Sex: Male and Female

Race: All

1. Provide target # of subjects (at all sites) needed to complete protocol.

For the Pilot Study, up to 6 adolescents and 6 parent(s)/guardian(s) may complete the study. These pilot subjects may also participate in the Main Study.

For the Main Study, 160 subjects (80 dyads – consisting of 80 adolescents and 80 adults) need to complete the study.

2. Describe expected rate of screen failure/ dropouts/withdrawals from all sites.

We expect that because the length of the study it could be 20-30% dropouts/withdrawals from the study.

3. How many subjects will be enrolled at all sites?

This is a single site clinical trial to be completed at UVa.

4. How many subjects will sign a consent form under this UVa protocol?

Up to 210 subjects (105 dyads – consisting of 105 adolescents and 105 parent(s)/guardian(s)) will sign consent for the Main Study and up to 16 subjects (8 parent/child dyads) will sign a consent for the Pilot Study. i.e. total = 226 (210+16)

Inclusion/Exclusion Criteria

1. List the criteria for inclusion for Pilot and Main Study Adolescent Subjects

- Willingness to provide informed consent
- Adolescents ages ≥ 12 and ≤ 17 years old with a parent/guardian (18+ yo) who is willing to participate with the child

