Study Objectives & Endpoint Definitions:

As mentioned previously, this project seeks to assess how CloudConnect affects participant engagement, dyad engagement, and clinical outcomes in adolescent T1D.

We will assess how adolescents and their parent(s)/guardian(s) respond to this new approach using the Family Communication Inventory (FCI). This diabetes-specific approach was designed by the investigators to assess parent-child communication regarding tasks (discussion of insulin dosing for a given meal, BG trends, need for dose changes). As an outcome measure, scores for parents and adolescents are summed, with higher scores representing higher degree of engagement and T1D-specific communication.

Power/Precision of the study to address major study endpoints:

In using the FCI, we determined based on preliminary data from 220 adolescent/parent participants eligible for the study, with mean (90.3) and standard deviation (12.5) that we are powered to detect a difference of 8.5% in this outcome in the treatment group with 80% power and an alpha of 0.05. This study will require 40 adolescent participants with 40 parent(s)/guardian(s) to complete per arm. Assuming a non-adherence/drop-out rate of 20-30% for Intention-to-Treat (ITT) analysis, 55 participants is yielded per arm.

3. Provide a justification for the sample size used in this protocol.

The study team will attempt to enroll an equal number subjects based on gender, CSII, and MDI use. The study is powered to detect a difference of 8.5% in this outcome in the treatment group with 80% power and an alpha of 0.05. This study will require 40 adolescent participants with 40 parent(s)/guardian(s) to complete per arm. Assuming a non-adherence/drop-out rate of 20-30% for Intention-to-Treat (ITT) analysis, 55 participants is yielded per arm.

4. What is your plan for primary variable analysis?

Because this is a randomized study, our primary outcome (score on the Family Communication Inventory) will be by t-test comparing those randomized to CloudConnect to usual care+CGM. Comparison of secondary outcomes between treatment groups will also be t-tests. Secondary analyses of both the primary and secondary outcomes will utilize multivariable ANOVA, particularly in the event that key variables differ between groups. For example, if average steps per day [as a measure of exercise] is higher in one group vs.

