Both groups will participate in the same number of visits (completed either in clinic or via phone or video conferencing) and follow up communication contacts done by phone calls, text messages and/or emails during the entire length of the trial. The production of the CloudConnect Report, in combination with the available Dexcom alarms and apps, is the study differential between groups.

*Secondary health outcomes: Average Blood Glucose values by Continuous Glucose Monitor; average total daily insulin; average carbohydrate of grams entered; number of insulin boluses; average number of steps by day

Figure 1: Study Design

There are four visits in the Main Study. Visit 1 and 2 may be combined and may be in person or via phone or video conference. A repeat Hemoglobin A1c will be collected if visit 1 and 2 are greater than 28 days. Visit 3 may be completed by phone. In addition, there will be weekly communication done by phone call, text message and/or email throughout the entire 12 weeks (3 months) of the data collection portion of the study. Method of weekly communications with the adolescent and parent will be based on participant/parent preference. The study team will communicate separately with the child and the parent in order to obtain their feedback independent of the other.

Subjects will be asked to electronically complete the following questionnaires at the completion of Visit 1 and repeated again at the conclusion of their study participation. Questionnaires may be answered remotely (i.e. at home) within a week of the visit or during a CRU visit.

- Blood Glucose Monitoring Communication questionnaire (Hood et al Diab Care 2004)
- Child and Parental Responsibility Questionnaire (adapted from Anderson et al J. Ped Psychol 1990)
- Child Self-Management
- Diabetes Care and Communication
- Diabetes Family Conflict Scale-Revised (Hood et al Diab Care 2007)
- Family Communication Inventory

- MY-Q (deWit et al Ped Diab 2012)
- Questions about CloudConnect use (CloudConnect group only, asked only at study end):
 - On a scale of 1-7, with 1 being very difficult and 7 being very easy, how easy was it to understand the information provided in the weekly reports? Can you tell me why you gave the score you did? What could have made the weekly reports easier to understand?

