Visit 2 (may be combined with Visit 1, may be done via phone or video): Adolescent subjects will be randomized and trained on the use of the study CGM and Fitbit. The CGM will be inserted into their abdomen per manufacturer instructions. Both Control and Experimental Group subjects will use their own personal pump. If the subject uses multiple daily injections (MDI), a commercially available Bluetooth connected insulin pen (inPen) will be given to both the Control and Experimental subjects in order to be able to collect the data accurately about meal time bolus treatments. Both pump users and MDI subjects will use their personal insulin. Each group will provide the study team weekly downloads from the study equipment and the personal insulin pump. Weekly CloudConnect reports will be provided to the Experimental Group participants *only*.

Depending on the subjects/family preference, the study team contact subjects via phone calls, text messages and/or emails at least once a week during the trial to:

- a) Remind them to download and transmit the data
- b) Check for AEs or SAEs
- c) Ask weekly standardized questions

All subjects will be reminded on how to download study data, if necessary. Both groups may complete a 1-week run-in period if they are CGM-naïve to ensure they are comfortable with the use of the study equipment, that all the study devices work properly, and to address issues related to transmission of the data to the study team. This run-in period may be repeated as necessary up to 3 times at the request of the study subject or study team. This data will not be included as part of the 12 week data collection. For subjects who have CGM experience, the investigator will determine if it is appropriate for he or she to skip the run-in period.

Visit 3 Check-in (Week 8 / on-site, email, or phone):

Subjects will download diabetes equipment weekly and submit the data to the study team for 12 weeks. Subjects may be asked to repeat a week of data collection if the quality of the data is insufficient for analysis.

A Check-In with the adolescent and parent/guardian will be completed to evaluate compliance and to answer any questions that the adolescent or parent may have about the study.

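### The primary FCI t-test leaves out a baseline FCI score that is already collected, and nothing requires that score to be in before open-label allocation

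*Combined protocol and SAP*

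**What the plan says.** **Primary analysis.** Statistical Considerations, item 4: "our primary outcome (score on the Family Communication Inventory) will be by t-test comparing those randomized to CloudConnect to usual care+CGM". No covariate is named. Item 2 defines the outcome as the sum of the parent and adolescent scores, one value per dyad.

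**Adjustment.** Item 4 continues: "Secondary analyses of both the primary and secondary outcomes will utilize multivariable ANOVA, particularly in the event that key variables differ between groups". Its examples are daily steps and insulin therapy, both in the comparison of mean CGM glucose. Baseline FCI is not mentioned.

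**Baseline measurement.** The Main Study section has subjects "electronically complete the following questionnaires at the completion of Visit 1 and repeated again at the conclusion of their study participation", and the FCI is on that list. It adds: "Questionnaires may be answered remotely (i.e. at home) within a week of the visit or during a CRU visit".

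**Order of events.** The same section says "Visit 1 and 2 may be combined and may be in person or via phone or video conference". Randomization belongs to Visit 2: "Adolescent subjects will be randomized and trained on the use of the study CGM and Fitbit". Study Design, item 2, states: "This is a randomized control, open-label, single-site clinical trial".

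**Hypothesis.** The Rationale expects that the CloudConnect group "will have a greater increase in engagement and dyad communication by 8 weeks that is sustained by 12 weeks (3 months".

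**The concern.** There are two linked points.

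1. **Efficiency and definition.** A baseline value of the primary outcome is requested from every dyad but is not in the primary model. Adjustment is left to a secondary analysis whose covariates are not fixed in advance and are prompted mainly by observed imbalance. Item 4 also does not say whether the score is the end-of-study value or the change from baseline. The Rationale speaks of an increase, while the mean of 90.3 and SD of 12.5 read as a score at one time.

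2. **Timing.** No passage requires the baseline FCI before allocation. If Visits 1 and 2 are combined and the family uses the one-week window, a self-reported baseline can be given after the family knows its arm. It would then not strictly be the pre-intervention level of engagement against which the Objectives/Hypothesis section promises to compare both arms.

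The points interact. A t-test on end scores ignores the baseline, so a late answer cannot harm it. ANCOVA and change scores both use the baseline, so improving the analysis without fixing the order of steps could bring in a bias that the present test does not have.

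**Working it through.** **Inputs from Statistical Considerations, item 2.** Mean 90.3; SD 12.5; difference 8.5%; 80% power; alpha 0.05; 40 completing dyads per arm. Difference = 0.085 × 90.3 = 7.6755 points, or 7.6755 / 12.5 = 0.614 SD.

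**Assumptions.** Two-sided test; the SD of 12.5 applies to the dyad sum at both times and in both arms. The baseline-to-end correlation ρ is not in the documents, so a range is shown.

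**The plan's own figure.** The normal approximation gives 42 per arm, and 78.4% power at 40, so the stated 40 reproduces to within rounding. With the exact (noncentral) t on 78 df:
- noncentrality = 7.6755 / (12.5 × √(2/40)) = 2.746, power 77.4%
- 42 per arm gives 79.4%; 43 per arm gives 80.4%
- difference detectable with 80% power at 40 per arm: 7.93 points (8.8% of 90.3)

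**ANCOVA and change score at 40 per arm.** ANCOVA residual SD = 12.5 × √(1 − ρ²), with 75 df (arm, baseline, age band, therapy) and no precision credited to the strata. Change-score SD = 12.5 × √(2(1 − ρ)), with 78 df.

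| ρ | ANCOVA SD | ANCOVA power | Change SD | Change power |
|---|---|---|---|---|
| 0 | 12.50 | 77.4% | 17.68 | 48% |
| 0.2 | 12.25 | 79.0% | 15.81 | 57% |
| 0.3 | 11.92 | 81.1% | 14.79 | 63% |
| 0.4 | 11.46 | 84.1% | 13.69 | 70% |
| 0.5 | 10.83 | 87.9% | 12.50 | 77% |
| 0.6 | 10.00 | 92.3% | 11.18 | 86% |
| 0.7 | 8.93 | 96.7% | 9.68 | 94% |

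- ANCOVA reaches 80% where 7.93 × √(1 − ρ²) = 7.6755, so ρ is about 0.25.
- The ANCOVA detectable difference is 7.77, 6.87 and 5.67 points (8.6%, 7.6%, 6.3%) at ρ = 0.2, 0.5 and 0.7.
- The change score is below ANCOVA at every ρ in the table, and no better than the plain t-test until ρ exceeds 0.5. At ρ = 0.3 the two readings of the score give 77% and 63% power.

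**Baseline answered after allocation.** If knowing the arm moves the average CloudConnect baseline by h points, the ANCOVA estimate moves by −ρh and a change score by −h. The value of h is an assumption.
- h = 2: ANCOVA bias is −0.6, −1.0 or −1.4 points at ρ = 0.3, 0.5 or 0.7 (8%, 13% or 18% of 7.68).
- h = 2, ρ = 0.5: expected estimate 7.68 − 1.0 = 6.68 points; power falls from 87.9% to 77.7%. Two-sided type I error rises from 5% to 6.9%: 6.0% in the tail favouring control and 0.9% in the tail favouring CloudConnect. With h = −2 the tails swap, and false claims for CloudConnect rise from 2.5% to 6.0%.
- ρ = 0.5 with h = 1 or 3: power 83.3% or 71.2%.
- h = 2 with ρ = 0.7: power 87.4%, still above the unadjusted test.

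A simulation of 20,000 trials agreed: at h = 2, ρ = 0.5, power 77.1% and type I error 7.2%.

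**The case against.** The strongest reply is that nothing in the stated primary test is wrong. Randomization justifies the t-test, and the sample size reproduces by the normal approximation. The shortfall from 80% is 1.6 points by that approximation and 2.6 by the exact t. The 0.25 threshold depends on that choice; by the normal approximation it is about 0.20. The benefit of ANCOVA rests on a correlation the documents do not give and is under 2 points at 0.2 or below. Item 4 also commits to adjusted secondary analyses and presents imbalance as an emphasis, not the sole trigger.

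On timing, the documents do give an intended order: questionnaires at the end of Visit 1, randomization at Visit 2, and pre-intervention engagement obtained at baseline. A late answer needs combined visits and use of the one-week window. It could not affect a t-test on end scores. The 2-point shift has no source and could go either way.

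All of this stands, and it limits the weight of the point: this is lost efficiency and an open path, not an error. It does not remove the point. The secondary analysis neither names baseline FCI nor is primary, the meaning of the score remains unstated, and no rule closes the path. One qualification concerns what a late answer could reflect. Both arms get the same device training and reports come weekly, so knowledge of arm should dominate. But alarms and apps are optional for controls, and the Main Study section counts them as part of the difference between arms.

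**Conclusion.** The concern holds. The primary test is valid but sets aside information already collected, and the schedule permits, without intending it, a baseline answered after open-label allocation.

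Pre-specified adjustment costs almost nothing if the correlation is nil: power stays at 77.4% to one decimal. It restores 80% at a correlation of about 0.25 and gives roughly 88% at 0.5. These figures assume 40 completers per arm, a common SD of 12.5 and a two-sided 0.05 test. The contamination figures rest on an assumed shift and show only that a modest one could cancel the gain at a correlation of 0.5. The change is worth making, but the trial does not become invalid without it.

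**What to change.** 1. **Order first.** Require both dyad members to submit the baseline questionnaires before the allocation is released, including when Visits 1 and 2 are combined.
2. **Primary model.** Pre-specify ANCOVA of the end-of-study dyad FCI on arm, baseline FCI, age band (12–14, 15–17) and insulin therapy (CSII, insulin pen). This also settles that the outcome is the end-of-study score. Keep the unadjusted t-test of that score as a sensitivity analysis; it does not depend on when the baseline was answered.
3. **Other outcomes.** Use the same form for the other questionnaire scores, and for HbA1c where a baseline exists. Because baseline HbA1c may be omitted under governmental restrictions, state one rule for it, for example imputing the overall mean without regard to arm and adding a missing-value indicator. This is secondary to the FCI point.

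The cost is a few sentences of analysis text and one check before allocation is released. No assessments or dyads are added.

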another, this will be used as a variable in the comparison of mean glucose by CGM to evaluate whether there remained a difference in mean glucose once total daily steps was taken into account. Similarly, if there is an imbalance of key participant characteristics among participants who complete the study in one treatment group (such as higher proportion of multiple-daily-injection participants in the CloudConnect group), this will be considered as a variable in the multivariable ANOVA comparing mean glucose by CGM, as a secondary analysis.

5. What is your plan for secondary variable analysis?

- HbA1c
- Mean glucose by CGM
- Percent time in range 70-180 mg/dL
- Percent time in range 70-150 mg/dL
- Percent time <70 mg/dL
- Percent time >180 mg/dL
- Number of low BG
- Average daily insulin dose
- Average grams of carbohydrate entered
- Steps/day by Fitbit
- Questionnaires: Family Conflict Scale, Division of Diabetes Responsibilities, Child Self Management and My-Q scores.
- Response to weekly standardized questions:
 - i. *During the past week, did you talk with your parents about your diabetes management?*
(Yes=1, No=2)
 - ii. If you answered “yes,” how good or bad was the tone of that conversation?
(Likert scale: Very good = 1; good =2; Neutral = 3 bad =4; Very bad =5)
 - iii. During the past week, did you change your insulin parameters?
(Yes=1, No=2)

6. Have you been working with a statistician in designing this protocol?

No

7. Will data from multiple sites be combined during analysis?

No

Study Procedures-Biomedical Research

1. What will be done in this protocol?

PILOT STUDY:

Up to six adolescent subjects and six parent(s)/guardian(s) will be enrolled in a Pilot Study to assess the components used by the Experimental Group of the Main Study. This trial will evaluate if: (i) subjects can be trained to use study CGM + study Fitbit + personal pump (if pump user) or study insulin pen for mealtime

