Visit 4 – End of Study (about Week 12): Subjects will be asked to return to the Clinical Research Unit (CRU) to return study equipment (i.e. Bluetooth pen, CGM, Fitbit), if possible. A post-study HbA1c test will be obtained with a point-of-care equipment or local laboratory (same method as screening collection). This can be omitted if it is not possible to go to a laboratory or come to the clinic because of governmental restrictions such as Stay-at-Home orders. Questionnaires will be completed electronically at the end of this visit. Questionnaires may be completed at home prior to this visit or at the CRU.

2. If this protocol involves study treatment, explain how a subject will be transitioned from study treatment when they have completed their participation in the study.

The study intervention is to evaluate the communication between the adolescent study subjects and their parents. The treatment for T1D is subcutaneous insulin either by using insulin pumps or insulin pens. This

treatment will remain the same at the completion of this study. Subjects will return to using their personal diabetes equipment and follow their own insulin parameters.

Subject Compliance with Study Procedures

- 1. Explain how the study team will monitor the subject for compliance with the study procedures.** A mid-study visit during Week 8 is planned to assess compliance. In addition, there will be at least 1 phone call or text message per week to remind subjects to download and transmit the required data, if needed.

It will be at the discretion of the investigator to determine if the patient is not compliant, i.e. three or more weeks with no data received, and the subject will be withdrawn for the study and replaced.

- 2. Describe criteria for when a subject is considered to be non-compliant with study procedures.**

The subject will be dismissed for the study if the subject misses 3 or more weeks of data downloads.

Bibliography

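### One unadjusted t-test rule for every secondary outcome does not suit the repeated weekly answers or the low-BG count, and leaves baseline values and strata unused

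*Combined protocol and SAP*

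**What the plan says.** Statistical Considerations, item 4, sets a t-test on the Family Communication Inventory as the primary analysis and continues: "Comparison of secondary outcomes between treatment groups will also be t-tests". No outcome is excepted. The only other model is a supplementary one: "Secondary analyses of both the primary and secondary outcomes will utilize multivariable ANOVA, particularly in the event that key variables differ between groups". It is described as covariate adjustment. Nothing is said about repeated measures, counts or exposure time.

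Item 5 asks for the secondary analysis plan and is answered with a list of variables. Most device measures carry their own per-participant basis (a mean, a percentage of time, a daily average). Two entries do not: "Number of low BG" and "Response to weekly standardized questions". The second covers three items: two yes/no questions coded 1 or 2, and a tone question coded "Likert scale: Very good = 1; good =2; Neutral = 3 bad =4; Very bad =5", asked only of those who report a conversation.

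Study Procedures, item 1 (Main Study), has these questions put every week for 12 weeks, to adolescent and parent separately. The same section places the questionnaires at Visit 1 and at the end of participation, and HbA1c at Visits 1 and 4 unless governmental restrictions prevent it. Statistical Considerations, item 1, defines four strata by age group and insulin therapy.

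**The concern.** A two-sample t-test needs one independent value per participant. For the weekly items the plan gives only codes for single answers, so an analyst must choose between averaging within a respondent, testing each week, or treating every answer as a separate record. These choices have very different error rates.

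A number of low BG values grows with the time observed. If the arms differ in observed time, the raw number differs even when the underlying rate does not.

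The weekly items also matter for a stated hypothesis. The rationale under Objectives/Hypothesis expects dyad communication to rise more with CloudConnect by week 8 and to hold to week 12. The questionnaires are not given at week 8, and Visit 3 is a compliance check, so the weekly answers are the only communication data at that time. One t-test on a 12-week average cannot address that timing.

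Finally, a plain t-test on HbA1c or a questionnaire score uses neither the participant's own baseline value nor the strata, although the trial plans to collect both.

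**Working it through.** **Inputs from the documents.** Completers: "This study will require 40 adolescent participants with 40 parent(s)/guardian(s) to complete per arm". Weekly contacts: 12. Alpha 0.05, taken as two-sided because the plan does not say. FCI mean 90.3, SD 12.5, difference 8.5%. Missed weeks: "The subject will be dismissed for the study if the subject misses 3 or more weeks of data downloads", so two missed weeks fall short of dismissal.

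**Assumed, because the documents give no value.** Intraclass correlation (ICC) of the weekly answers, 0.05 to 0.5. Probability of a 'yes', 0.1 to 0.95. Rate and between-person spread of lows, as given in step 4.

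**Step 1: the plan's own figure.** The plan gives no error rate for secondary outcomes. Its one checkable figure is the 40 per arm for the primary t-test. The difference is 0.085 × 90.3 = 7.68 points. Then n = 2 × (1.96 + 0.84)² × 12.5² / 7.68² = 41.5, so 42 per arm. Power at 40 is Φ(7.6755 / (12.5 × √(2/40)) − 1.96) = Φ(0.786) = 78.4%. This agrees with the stated 40 and 80% to within two participants and two percentage points.

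**Step 2: weekly answers pooled as records.** This gives 40 × 12 = 480 records per arm. The true variance of the arm mean exceeds the one the t-test assumes by D = 1 + 11 × ICC, so the actual type I error is 2 × [1 − Φ(1.96/√D)].

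| ICC | D | 1.96/√D | Formula | Simulated, yes/no | Simulated, five-level |
|---|---|---|---|---|---|
| 0.05 | 1.55 | 1.574 | 11.5% | 11-12% | not run |
| 0.1 | 2.1 | 1.353 | 17.6% | 16-18% | 16% |
| 0.3 | 4.3 | 0.945 | 34.5% | 34-35% | 32% |
| 0.5 | 6.5 | 0.769 | 44.2% | 44-45% | 43% |

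Each simulated setting used 5,000 null trials of 40 against 40 with complete answers. The five-level column therefore ignores that tone is recorded only after a 'yes'.

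**Step 3: the other two readings.** With one summary per participant (share of 'yes' weeks, mean tone), the t-test has a type I error of 4.3-5.3% for yes/no items and 4.8-5.2% for the five-level item. With a separate t-test in each of the 12 weeks, the chance of at least one p < 0.05 is 28-52%.

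**Step 4: number of lows.** Overdispersed (gamma-Poisson) counts were simulated with no arm difference in the true rate.
- One total per participant, equal observation time: 4.3-5.1%. Skewness alone does no harm to the error rate at 40 per arm.
- One total per participant, 12 weeks in one arm and 11 in the other, mean 1 or 5 lows per week, gamma shape 2 or 5: 8-13%. The expected totals differ by 12/11, about 9%.
- The same with 12 against 10 weeks: 18-41%. The expected totals differ by 12/10, or 20%.
- Lows per observed week, in the same unequal settings: 4.7-5.2%.
- Weekly counts pooled as records: 28-54%.

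The 12-against-10 case has every participant in one arm observed for two weeks less, so it is an outer case.

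**Step 5: baseline and strata.** An unadjusted t-test in a randomised trial keeps its error rate, so the issue here is precision. For an end-of-study value, ANCOVA on baseline multiplies the residual variance by about 1 − r², where r is the baseline-to-end correlation. The documents do not give r, so no figure is put on the gain.

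**The case against.** A reader might infer that the plan commits to an analysis with a false-positive rate of up to 44%. It does not. Nothing says the weekly answers will be pooled. The neighbouring outcomes are per-participant summaries and the comparison is described as one between randomised participants, so one value per person is at least as natural a reading. That reading holds about 5%. Nor does yes/no or five-level coding invalidate a t-test at this size. Giving each participant equal weight, however many answers they gave, is a legitimate choice.

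A reader might also infer that a count inflates the error by its nature, or that weekly reports lead to longer sensor wear in the CloudConnect arm. The first is contradicted by step 4. The second is not in the documents: both arms receive the same CGM and the same download reminders, weeks of insufficient data may be repeated, and prolonged non-submission leads to dismissal. The list also contains percent time below 70 mg/dL, which is already scaled to observed time.

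All of this stands, and it removes any claim of a built-in error. It does not supply the missing definitions. The safeguards limit differences in observed time without excluding them: up to two weeks can be missed, and 20-30% dropout is expected. The supplementary ANOVA is prompted chiefly by observed imbalance, so it does not amount to prespecified adjustment for baseline and strata.

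**Conclusion.** The point holds as a mismatch between the stated method and several of the outcomes, together with two missing definitions: the unit of analysis for the weekly items and the exposure basis for lows. Of the three readings the text permits for the weekly items, one holds about 5%. Pooling gives about 12-44%, conditional on an assumed ICC of 0.05 to 0.5, and week-by-week testing gives 28-52% for any false positive. For lows, a raw total is sound with equal observation time. It rises to 8-13% or 18-41% only if one arm is observed for one or two weeks less, under the assumed rates and spread. The omission of baseline and strata costs precision, not validity.

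These are secondary outcomes, and the primary t-test is unaffected. The change is still worth making before outcome data are compared, because the weekly items are the only source for the week-8 communication hypothesis.

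**What to change.** Replace the single t-test sentence in Statistical Considerations, item 4, with a rule for each type of outcome.

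1. **Weekly yes/no items.** A logistic GEE or mixed model clustered on the respondent, with arm, week, arm-by-week and the randomisation strata, and named contrasts at weeks 8 and 12. At minimum, one proportion per participant. Say whether parents' answers are included, since item 5 lists only the adolescent wording. Analyse adolescents and parents separately, or cluster on the dyad if they share a model.
2. **Tone item.** A per-participant mean or an ordinal mixed model, reported as conditional on a 'yes', which is itself a post-randomisation answer.
3. **Number of low BG.** A rate per unit of CGM wear time: negative binomial regression with log wear time as offset.
4. **HbA1c and questionnaires.** ANCOVA on the baseline value and strata, with a simple stated rule for participants whose baseline HbA1c was omitted.
5. **Other continuous outcomes.** A linear model with the strata.

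The cost is a paragraph of text and slightly more analysis work in standard software. No new data are needed, provided that CGM wear time is taken from the weekly downloads.
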